6.7 Secondary Endpoints

Secondary outcome measures include:

- Average daily minutes of VR or sham use at during weeks 1-4 and weeks 1-8.
- Number of days VR or sham used.
- Number of days that participants completed all outcome assessments.
- Patient satisfaction score (min 3 – max 12).
- Likelihood of recommending VR treatment to someone else (min 1 – 10 max).
- Number of adverse events related to the study treatment.
- Change from baseline PSEQ-2, PCS-4, CPAQ-8, SF-12 score at 4, 8, and 12 weeks.
- Change from baseline in total ODI score as well as subscale scores at 4, 8, and 12 weeks.
- Average self-reported daily amount of analgesic medication used during weeks 1-4 and weeks 1-8.
- Total milligrams of morphine equivalent doses filled from PDMP database at 3 months, 6 months, and 12 months.
- Total number of office visits, admissions, emergency room visits, and therapy sessions related to the patient's lower back pain at 3 months, 6 months, and 12 months.
- Total cost of care related to patient's lower back pain at 3 months, 6 months, and 12 months.

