6 STUDY DESIGN

6.1 Description

This is a single-center, prospective, randomized, double-blind, placebo-controlled study of the appliedVR EaseVRx headset in subjects with chronic lower back pain. A cohort of 126 patients will be recruited from patients currently seeking care for low back pain at Geisinger. We are assuming a 20% dropout or noncompletion rate, so recruiting 126 patients should provide 100 completes. Patients with moderate to severe chronic low back pain who have largely exhausted non-pharmacological approaches to improving pain and who are currently relying primarily on pharmacotherapy for symptom relief will be recruited for the study. These patients are an ideal study population to include as few treatment options remain for these patients due to insufficient understanding of pain origin, failure of conventional pain management approaches, or unsuitability of surgical interventions. Patients will be randomized by computer 1:1 to either the VR sham or EaseVRx group. Providers and patients will be blinded in regard to whether the patient will receive EaseVRx or the VR sham.

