Outcomes data also may be collected via REDCap, a secure research electronic data capture system, or OBERD, a software system for patient-reported outcomes already in use at the study clinics. To assess opioid use, the investigators will query Pennsylvania's Prescription Drug Monitoring Program (PDMP) database. To maintain compliance with ABC-MAP Act 191 of 2014, study investigators will query the PDMP only for their existing patients. Patient clinical information will be extracted from their electronic medical records, including patient demographics, medical history and prescription information.

The EaseVRx devices will collect information related to device usage (i.e. frequency and duration of use, features utilized, completion rates). Patients may be contacted via phone or email by the study team to further encourage participation.

Outcome measures include:

- **Program Feasibility:**
 - Patient compliance will be assessed in two ways:
 - Treatment dose (actual minutes of VR or sham use per day); and
 - Treatment duration (actual number of days VR or sham used).
 - Program retention will be evaluated by the number of days that participants completed all outcome assessments.
 - Patient satisfaction will be assessed once at the end of the program by asking the participant four questions to evaluate the program:
 - Please tell me if you agree or disagree with the following statements:
[strongly agree, somewhat agree, somewhat disagree, strongly disagree]
 - The VR headset was easy to use.
 - I enjoyed using the VR headset.
 - The content in the VR headset helped me cope with my chronic pain.
 - Today, on a scale of 1 to 10, where 1 means you would definitely NOT recommend VR treatment and 10 means you WOULD definitely recommend VR treatment, how likely are you to recommend VR treatment to someone else?
 - Patient safety will be assessed by monitoring subjects for the occurrence of adverse events (AE).
- **EaseVRx Efficacy:**

- Pain will be assessed via the standard Geisinger Numerical Pain Rating Scale (NPRS) ranging 0-10 (0 = least amount of pain, 10 = worst amount of pain).
- Pain Coping Skills will be assessed via:
 - Pain Self-Efficacy Questionnaire (PSEQ-2)^{114, 115}, which measures the confidence people with ongoing pain have in performing activities while in pain;
 - Pain Catastrophizing Scale (PCS-4)¹¹⁶, which measures the impact of catastrophizing on the pain experience; and

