6.8.1 Statistical Analysis Plan

We will calculate frequencies for categorical data and means with standard deviations for continuous variables. Bivariate comparisons will be explored using Chi-square or Fisher's exact test for categorical variables and two-sample t-tests or Mann-Whitney tests for continuous variables.

Because pain is expected to decrease over time, and because pain scores may vary by day and time of day administered, we will plan to plot NPRS score vs. time for every patient over the 8-week treatment period, using straight-line interpolation between measurements, which will allow us to use all available measurements (even if some patients recorded more NPRS scores than others) and will avoid placing too much emphasis on a measurement at a single time point (e.g. the 21-day measurement). We will compute a percent-area-under-the-curve (NPRS-%AUC)

measurement where 100% would indicate pain scores of 10 across the entire time period. Each patient will have a different NPRS-%AUC, forming a distribution of measures in each of the two groups, and we will use an unpaired t-test to compare the mean NPRS-%AUC for patients before and after the intervention.

Percent change in PSEQ-2, PCS-4, CPAQ-8, ODI, SF-12 and total opioid usage (measured in MME) will be compared between groups using ANOVA, or, if more appropriate, a nonparametric Kruskal-Wallis test.

Covariates in the analysis of covariance models include study site, sex, duration of pain, opioid use, and baseline outcome scores.

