7 SAFETY MONITORING

7.1 Adverse Event Reporting

Clinical adverse events (AEs) will be monitored throughout the study. All AEs will be reported to the institutional review board (IRB) regardless of whether they are considered study related. The date and time of onset and outcome, course, intensity, action taken, and causality to study treatment will be assessed by the study PI. In the event of a serious AE (SAE), this will be reported to the Geisinger IRB (GIRB) according to the GIRB guidelines. All other AEs will be summarized and submitted to GIRB during continuing review.

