7.2 Definitions

An **adverse event** (AE) is any untoward, undesired, or unplanned event in the form of signs, symptoms, disease, or laboratory or physiologic observations occurring in a person given a test article or in a clinical study. The event does not need to be causally related to the test article or clinical study.

No technical difficulties are anticipated in the performance of these studies; the methods in place are similar to other appliedVR product proof-of-concept studies previously conducted in hospital settings, which revealed no adverse events.

The potential risks posed by EaseVRx to the patient are limited, as the EaseVRx does not control any diagnosis or medical decisions and the patient is free to suspend or halt use at any time by removing the VR headset. The primary risk is that the patient does not respond to EaseVRx and continues to feel pain. Other risks include minor adverse events such as motion sickness, vertigo, nausea, vomiting, or panic attacks. Again, these rare adverse events can be remedied by removing the VR headset. EaseVRx includes a wide range of experiences to allow for patients with phobias or triggers for panic attacks to choose other experiences which do not incorporate those factors.

A **serious adverse event** (SAE) is an AE that:

- Results in death.

- Is **life-threatening** (see below).
- Requires inpatient hospitalization or prolongation of an existing **hospitalization** (see below).
- Results in a persistent or significant **disability** or incapacity (see below).
- Results in cancer.
- Results in a congenital anomaly or birth defect.
- Additionally, important medical events that may not result in death, be life-threatening, or require hospitalization may be considered SAEs when, based on appropriate medical judgment, they may jeopardize the subject and may require medical or surgical intervention to prevent one of the outcomes listed in this definition. Examples of such events include allergic bronchospasm requiring intensive treatment in an emergency room or at home, blood dyscrasias or convulsions that do not result in hospitalization, or development of drug dependency or drug abuse.

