7.3 Recording and Reporting

A subject's AEs and SAEs will be recorded and reported from the signing of the informed consent form to the completion of post-treatment outcome measures collection at 3 months.

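### The only adverse-event endpoint in 6.7 is a number of treatment-related events, which is narrower than the safety outcome in 6.5 and gives no proportion of patients affected

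*Combined protocol and SAP*

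**What the plan says.** Section 6.7 lists twelve secondary outcome measures. One concerns AEs: "Number of adverse events related to the study treatment". None covers AEs of any cause, serious AEs, or patients with at least one AE.

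Other sections are broader:

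- Section 6.5, outcome measures: "Patient safety will be assessed by monitoring subjects for the occurrence of adverse events (AE". No relatedness limit and no counting unit are given.
- Section 7.2, AE definition: "The event does not need to be causally related to the test article or clinical study".
- Section 7.1: "All AEs will be reported to the institutional review board (IRB) regardless of whether they are considered study related". The same section says "causality to study treatment will be assessed by the study PI". It gives no attribution criteria.
- Section 7.3: recording runs "from the signing of the informed consent form to the completion of post-treatment outcome measures collection at 3 months".

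On blinding, section 6.1 says "Providers and patients will be blinded in regard to whether the patient will receive EaseVRx or the VR sham". Whether the PI is blinded when judging causality is not stated. Section 6.8.1 assigns no analysis to AEs. It offers general tools only: "Bivariate comparisons will be explored using Chi-square or Fisher's exact test for categorical variables", and t-tests or Mann-Whitney tests for continuous variables.

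**The concern.** Safety is a named part of the feasibility aim (Secondary Aim 3), and the study is meant to prepare for a larger trial. The trial has a randomized sham arm that controls for wearing a headset. Comparing the frequency of all AEs between the arms would show whether the active content adds harm, without anyone having to decide what caused each event. An endpoint limited to events judged related gives up that advantage: an event attributed to back pain or to medication drops out of it.

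The wording also yields a number of events and no proportion of patients. The expected events in 7.2, such as motion sickness and nausea, can recur from one use to the next. A total therefore does not show whether many patients had one event each or a few had many. Planning a larger trial needs the proportion.

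**Working it through.** **1. Scope.** Sections 6.5, 7.2 and 7.1 cover any AE, whatever its cause. Section 6.7 covers only the subset that the PI calls related. The difference is the set of AEs judged unrelated. It is recorded and sent to the IRB, but it enters no endpoint. The documents do not say how large it might be.

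**2. Denominators.** Sections 6.1 and 6.2.1 give 126 participants, 63 per arm, with 20% dropout. Check: 100 / (1 − 0.20) = 125, and 126 × 0.80 = 100.8, so the plan's 100 completers are reproduced. An even split is 50 per arm. There is no AE rate, so the safety endpoint has no planned figure to reproduce. All rates below are assumptions.

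**3. Effect of the relatedness filter.** Let p be the true risk of an AE in an arm and q the share called related. The observed risk is p × q. Approximate power, with n per arm, two-sided 5% and p̄ the mean of the two observed risks, is

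Φ{ [ |p1 − p2| − 1.96 √(2p̄(1 − p̄)/n) ] / √[ (p1(1 − p1) + p2(1 − p2))/n ] }.

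| True risks | Called related | Observed risks | Power, n = 50 | Power, n = 63 |
|---|---|---|---|---|
| 30% v 15% | all | 30% v 15% | 0.43 | 0.52 |
| 30% v 15% | 80% v 80% | 24% v 12% | 0.34 | 0.42 |
| 30% v 15% | 50% v 50% | 15% v 7.5% | 0.22 | 0.26 |
| 30% v 15% | 40% v 80% | 12% v 12% | no difference left | no difference left |
| 30% v 30% | 80% v 60% | 24% v 18% | 0.11 | 0.13 |
| 30% v 30% | 80% v 40% | 24% v 12% | 0.34 | 0.42 |

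In the last two rows the true risks are equal, so the power column is the chance of a false difference. Equal attribution in both arms loses events and information. Only unequal attribution hides or creates a difference.

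**4. Repeat reporters, if events are totalled.** Section 6.5 assigns 5 modules a week for 8 weeks, so 8 × 5 = 40 modules. Suppose 10 of 50 patients in each arm have one event. The patient-level comparison is 10 v 10 (Fisher p = 1.00). Now let one of those patients log extra events, and test the totals as if events were independent (exact binomial, half expected in each arm):

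| Extra events from one patient | Totals | p |
|---|---|---|
| 5 | 15 v 10 | 0.42 |
| 10 | 20 v 10 | 0.099 |
| 15 | 25 v 10 | 0.017 |
| 20 | 30 v 10 | 0.002 |

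The patient-level result stays at 10 v 10 throughout.

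**5. Does the unit matter for a test?** Trials were simulated with no true difference (4,000 per setting, 50 per arm, mean 0.3 or 0.6 events per patient). Counts were Poisson, or negative binomial with variance m + m²/k, where m is the mean and k the dispersion parameter. Variance inflation is 1 + m/k, here 1.3 to 3.4. Rejection rates at 5%:

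| Test | No clustering | With clustering |
|---|---|---|
| Raw event totals | 0.030 to 0.039 | 0.058 to 0.248 |
| Fisher, patients with at least one event | 0.027 to 0.037 | 0.028 to 0.035 |
| t-test on per-patient counts | 0.048 to 0.049 | 0.042 to 0.048 |

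The inflation arises only for a test on raw totals, and the plan names no such test.

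**The case against.** A reader might infer that the sham-controlled safety comparison is compromised. The documents do not support that. Secondary Aim 3 is worded as an assessment of EaseVRx, whereas the other aims are worded as comparisons between groups, and 6.8.1 assigns no test to AEs.

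A reader might also infer that active-arm harms would be under-reported. A biased contrast needs attribution that differs by arm. Patients and providers are blinded, and the PI may be a blinded provider, although this is not stated. Section 7.2 also names nausea and motion sickness as device risks, which makes it less likely that they would be attributed elsewhere.

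A third inference is that one patient could add 40 events. That is a theoretical ceiling. Nothing says each module is a separate sitting, 6.2.2 excludes people prone to nausea or sensitive to motion, and 7.2 calls such events rare and relieved by taking off the headset. The neighbouring items in 6.7 are per-participant measures, so the AE item may be one too. A Mann-Whitney test would then give a repeat reporter a single rank, and the t-test held its error rate above.

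Finally, no safety data are lost, and the broader wording in 6.5 suggests that 6.7 may simply be loosely phrased.

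All of this stands as a limit on the consequences. It does not change two facts about the endpoint: AEs judged unrelated fall outside it, and under either reading it gives no proportion of patients affected.

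**Conclusion.** The point holds as a gap between the endpoint in 6.7 and both the safety outcome in 6.5 and the data recorded under 7.1 to 7.3. Followed as written, the endpoint depends on the PI's causality judgement, leaves the sham arm unused as an attribution-free reference, and does not show how many patients were affected. Skew from repeat reporters is conditional on events being totalled by arm. Bias between arms is conditional on attribution differing by arm. Neither is established by the documents.

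The size cannot be stated, because no AE rate, attribution share or degree of clustering is given; the figures above show only how the result moves under assumed values. The matter is minor: one secondary endpoint in a proof-of-concept study, with no bearing on the primary efficacy analysis and no decision rule attached.

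**What to change.** Restate the AE endpoint in 6.7 as the number and percentage of randomized participants in each arm with at least one AE, shown for all causes and separately for treatment-related and serious AEs. Give event counts as a supplement. This brings 6.7 into line with 6.5 and supplies patient-level rates for the planned larger trial.

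Two clarifications would help. State in 7.1 whether the PI is blinded when judging causality. Also reconcile the events table in 6.5.1, whose AE row as extracted is marked only to 4 weeks, with the 3-month window in 7.3; the table may have been damaged in extraction.

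The cost is a reworded line in 6.7 and one added table. The data are already to be recorded under 7.1 to 7.3, so no new collection is needed.

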4 HYPOTHESIS AND SPECIFIC AIMS

4.1 Primary Aim 1

Compare pain and pain coping skills among the VR sham and the EaseVRx group. *Hypothesis: Chronic low back pain patients randomized to the EaseVRx approach who use the device in accordance with the treatment protocol will have significantly decreased pain scores and improved pain coping skills 4, 8, and 12 weeks after starting the 8-week VR treatment.*

4.2 Secondary Aim 1

Compare physical function as measured by the Oswestry Disability Index (ODI) among the VR sham and EaseVRx group. *Hypothesis: Chronic pain patients randomized to the EaseVRx approach who use the device in accordance with the treatment protocol will have significantly better physical function (i.e. lower ODI scores) 4, 8, and 12 weeks after starting the 8-week VR treatment.*

4.3 Secondary Aim 2

Compare analgesic medication use among the VR sham and EaseVRx group. *Hypothesis: Chronic pain patients randomized to the EaseVRx approach who use the device in accordance with the treatment protocol will have decreased utilization of opioid and non-opioid pharmacotherapy 4, 8, and 12 weeks after starting the 8-week VR treatment.*

4.4 Secondary Aim 3

To assess the feasibility of EaseVRx as a self-administered, home-based approach to chronic pain management, in terms of patient compliance, program retention, patient satisfaction, and safety. *Hypothesis: EaseVRx will be a feasible approach to chronic pain management, with high rates of patient compliance, retention, and satisfaction among chronic pain patients after completing an 8-week course of treatment with EaseVRx.*

4.5 Secondary Aim 4

Compare healthcare cost and utilization among the VR sham and EaseVRx group among patients with Geisinger Health Plan as their primary insurance. *Hypothesis: Chronic pain patients randomized to the EaseVRx approach who use the device in accordance with the treatment protocol will have significantly lower costs and utilization (i.e. office visits, therapy sessions, inpatient/ED admissions) 3 months, 6 months, and 12 months after starting the 8-week VR treatment.*

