 - Chronic Pain Acceptance Questionnaire (CPAQ-8)^{117, 118}, which measures the ability to accept and cope with chronic pain.
- Physical function will be assessed using by the Oswestry Disability Index (ODI).
- Analgesic medication use will be assessed in two ways:
 - Extrapolating total milligrams of morphine equivalent doses filled from PDMP database as an indicator of chronic opioid use; and
 - Patient self-reported consumption.
- Quality of life will be assessed using the 12-item Short Form Health Survey (SF-12).
- **Healthcare Cost and Utilization** (*Geisinger Health Plan patients only*):
 - Utilization will be assessed by recording the number of office visits, admissions, emergency room visits, and therapy sessions related to the patient's lower back pain for 12 months. Total milligrams of morphine equivalent doses filled from PDMP database also will be tracked.
 - Cost will be assessed by recording actual total amounts allowed by Geisinger Health Plan (GHP) and paid to the health system, by both insurer and patient, for utilization, medication, and other costs related to the patient's lower back pain.

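### PDMP opioid totals at 3, 6 and 12 months, which read as cumulative, are analysed as percent change with no matching baseline period, so effect size depends on window length and the 12-month value alone cannot show persistence

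*Combined protocol and SAP*

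**What the plan says.** Section 6.7 makes the following a secondary endpoint: "Total milligrams of morphine equivalent doses filled from PDMP database at 3 months, 6 months, and 12 months". It gives no start or end for any of the three windows. Section 6.5 describes the measure's purpose as "Extrapolating total milligrams of morphine equivalent doses filled from PDMP database as an indicator of chronic opioid use", and under utilization, which is recorded for 12 months, adds "Total milligrams of morphine equivalent doses filled from PDMP database also will be tracked".

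Section 6.8.1 sets the analysis: "Percent change in PSEQ-2, PCS-4, CPAQ-8, ODI, SF-12 and total opioid usage (measured in MME) will be compared between groups", by ANOVA or Kruskal-Wallis. It names no time point and no baseline window for the opioid measure. The same section lists opioid use and baseline outcome scores as ANCOVA covariates, also without a window. The table in 6.5.1 ticks analgesic use at Day 0 but gives no look-back length. The only baseline period that the plan defines is the one-week NPRS average in 6.6.

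Two statements in section 4 bear on timing. Secondary Aim 2, on medication, expects that patients "will have decreased utilization of opioid and non-opioid pharmacotherapy 4, 8, and 12 weeks after starting the 8-week VR treatment". Secondary Aim 4, on cost and utilization, counts "3 months, 6 months, and 12 months after starting the 8-week VR treatment".

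**The concern.** A percent change in fills needs a denominator taken over a stated period, and fills cannot be totalled over a single day. If the numerator covers 3, 6 or 12 months and the denominator covers some other fixed period, the result mixes change in use with the ratio of the two window lengths. An analyst would have to choose the look-back, and that choice sets the size of the reported effect.

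The second issue is nesting. If each total runs from the start of treatment, the 6- and 12-month values contain the 8-week program. The device is returned at the end of that program (6.5), so whether lower use persists is a natural question for the later time points. A difference in the 12-month total could be read as a lasting opioid-sparing effect when use differed only early on.

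Third, opioid use is not an entry criterion (6.2.2). Patients with no opioid fills at baseline are eligible, and their percent change is undefined.

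**Working it through.** The documents contain no opioid level, variability or expected effect, so there is no opioid figure to reproduce. The look-back lengths and the 20% reduction below are assumptions. Only the 3-, 6- and 12-month time points and the 8-week program come from the plan.

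**Step 1: unchanged use, cumulative totals.** Let a patient fill the same MME every month before and after Day 0. A total over m months against a look-back of L months gives percent change = 100 × (m/L − 1).

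| Assumed look-back L | 3 months | 6 months | 12 months |
|---|---|---|---|
| 1 month | +200% | +500% | +1100% |
| 3 months | 0% | +100% | +300% |
| 6 months | −50% | 0% | +100% |
| 12 months | −75% | −50% | 0% |

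The change is zero only where m = L. Any single L therefore leaves a non-zero value at two or more of the three time points.

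**Step 2: unchanged use, interval totals.** If the totals instead cover months 0-3, 3-6 and 6-12, the windows are 3, 3 and 6 months long. With L = 3 the values are 0%, 0% and 100 × (6/3 − 1) = +100%. The artefact is smaller but does not vanish.

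**Step 3: a sustained 20% cut against sham, cumulative totals.** Two scales must be kept apart.
- Points of percent change: 20 × m/L. With L = 3 the gap is 20, 40 and 80 points. With L = 12 it is 5, 10 and 20 points.
- Relative to the sham total: 20% at every time point, whatever L is.

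The same true effect thus gives 80 or 20 points at 12 months, depending only on the look-back.

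**Step 4: a 20% cut confined to months 0-3, cumulative totals.**
- Relative to the sham total: 20 × 3/m = 20%, 10% and 5% at 3, 6 and 12 months.
- Points of percent change with L = 3: 20 × 3/3 = 20 points at all three time points, because the ended difference stays in the numerator and the denominator is fixed.
- If the cut lasts 2 months (about the 8-week program), the share of the sham total is 20 × 2/m = 13.3%, 6.7% and 3.3%.

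A 5% cut sustained for 12 months also gives 5% of the sham 12-month total. That value alone cannot tell the two patterns apart.

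**Step 5: average daily MME in separate intervals (0-3, 3-6, 6-12).** Unchanged use gives no change in any interval. A 20% cut ending at month 3 gives 20%, 0% and 0%. A sustained 20% cut gives 20%, 20% and 20%.

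**The case against.** - **The link between 6.7 and 6.8.1 is inferred.** The PDMP line in 6.7 does not mention change from baseline, although the questionnaire and ODI lines do, and 6.8.1 names neither the PDMP nor the three time points. Its opioid measure could be diary use. This is possible, but the plan uses MME totals only for PDMP fills (6.5, 6.7), while 6.7 gives self-reported use as an average daily amount. If the PDMP totals were compared raw, the percent-change problem would go and the carry-over would stay.
- **Cumulative counting is not stated.** This stands. A reader might infer that 6.7 defines a running total, but it does not say so. The reading is supported by the word total, by the time origin in Secondary Aim 4, and by the nested windows used elsewhere (weeks 1-4 and 1-8).
- **Both arms share the window.** This stands. A reader might infer a biased treatment comparison, but the documents do not support that. The factor m/L is common to both arms, and under steady pre-baseline use a common scale factor leaves the ANOVA or Kruskal-Wallis result unchanged.
- **Interval amounts can be recovered by subtraction.** This also stands if cumulative totals are held at all three times. The limitation belongs to the 12-month value as an endpoint, and the plan does not call for the subtraction.
- **Aim 2 makes no claim beyond 12 weeks.** This is correct, yet 6.7 still sets the 6- and 12-month endpoints.

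**Conclusion.** The point holds on the natural reading that the totals accumulate from treatment start and that the percent change in 6.8.1 applies to them. On that reading the reported percent change is arbitrary in size and cannot be compared across time points: with an assumed 3-month look-back, unchanged use scores 0%, +100% and +300%. An ended 20% cut in months 0-3 remains as 10% and 5% of the sham total at 6 and 12 months. Separately, and on either reading of the windows, percent change is undefined for eligible patients with no baseline fills; the documents do not say how many there would be.

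The harm is to interpretation, not to the validity of the randomised test. A reader might also infer that the PDMP is the only objective source on opioid use. It is one of the two measures of analgesic use that 6.5 specifies, and the one not self-reported, but 6.5 also extracts prescription information from the medical record. This is one secondary endpoint of a proof-of-concept study. The change is worth making because it is cheap and yields a better-defined measure.

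**What to change.** In 6.7, replace the three totals with average daily MME filled (MME filled divided by days in the interval) for months 0-3, 3-6 and 6-12 from treatment start. The self-report endpoint in 6.7 already uses a daily average, so the form is not new to the plan.

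In 6.8.1, drop percent change for this endpoint. Compare the arms on each interval's average daily MME, adjusted for average daily MME over the 3 months before Day 0 from the same PDMP query. This gives the already listed opioid-use covariate a definition and keeps patients with zero baseline fills in the analysis. The cumulative 12-month total may stay as a description.

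In the same edit, reconcile the 4, 8 and 12 weeks of Secondary Aim 2 with the 3, 6 and 12 months of the endpoint.

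The cost is endpoint and SAP wording plus a look-back in queries that are already planned. The downside is some precision: a single interval holds fewer fills than a cumulative total, so its estimate is somewhat noisier. Months 0-3 will still mix the 8-week program with the weeks just after it; the two later intervals are wholly post-treatment.
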